7.2.1. Discontinuation of Inadvertently Enrolled Participants

If the sponsor or investigator identify a participant who did not meet enrollment criteria and was inadvertently enrolled, then the participant should be discontinued from study treatment unless there are extenuating circumstances that make it medically necessary for the participant to continue on study treatment. If the investigator and the sponsor clinical research physician (CRP) agree that it is medically appropriate to continue, the investigator must obtain documented approval from the sponsor CRP to allow the inadvertently enrolled participant to continue in the study with or without treatment with investigational product.

Safety follow-up is as outlined in Section 1.3 (Schedule of Activities), Section 8.2 (Safety Assessments), and Section 8.3 (Adverse Events and Serious Adverse Events) of the protocol.

7.3. Lost to Follow-up

A participant will be considered lost to follow-up if he or she loses contact with the study site for more than 10 days. Site personnel are expected to make diligent attempts to contact participants who fail to return for a scheduled visit or were otherwise unable to be followed up by the site.

8. Study Assessments and Procedures

- Study procedures and their timing are summarized in the SoA. Protocol waivers or exemptions are not allowed.
- Immediate safety concerns should be discussed with the sponsor immediately upon occurrence or awareness to determine if the participant should continue or discontinue study intervention.
- Adherence to the study design requirements, including those specified in the SoA, is essential and required for study conduct.
- All screening evaluations must be completed and reviewed to confirm that potential participants meet all eligibility criteria. The investigator will maintain a screening log to record details of all participants screened and to confirm eligibility or record reasons for screening failure, as applicable.

8.1. Efficacy Assessments

8.1.1. Primary Efficacy Assessments

The primary efficacy measure is the change from baseline in percentage of time with sensor glucose values between 70 and 180 mg/dL (both inclusive), from CGM use in the maintenance period.

8.1.2. Secondary Efficacy Assessments

Secondary efficacy assessments for this study are

- Change from baseline in ICR at the end of the maintenance period
- ICR×TDD for the maintenance period
- Prandial:TDD ratio for the maintenance period

8.2. Safety Assessments

Planned time points for all safety assessments are provided in the SoA Section 1.3.

The actual and change from baseline in percentage of time with sensor glucose values <54 mg/dL will be evaluated with CGM as an exploratory objective.

8.2.1. Physical Examinations

A complete physical examination will include, at a minimum, assessments of the cardiovascular, respiratory, gastrointestinal, and neurological systems. Height and weight will also be measured and recorded.

Investigators should pay special attention to clinical signs related to previous serious illnesses.

8.2.2. Vital Signs

For each participant, vital signs measurements should be conducted according to the Schedule of Activities (Section 1.3).

8.2.3. Electrocardiograms

Single 12-lead ECG will be obtained as outlined in the SoA (see Section 1.3) using an ECG machine that automatically calculates the heart rate and measures PR, QRS, and QT.

8.2.4. Clinical Safety Laboratory Assessments

See Section 10.2 (Appendix 2) for the list of clinical laboratory tests to be performed and to the SoA for the timing and frequency. See Section 10.5 (Appendix 5) for clinical laboratory testing for close hepatic monitoring and see Section 10.2.1 for clinical laboratory testing for hypersensitivity.

The investigator must review the laboratory report, document this review, and record any clinically relevant changes occurring during the study in the AE section of the CRF. The laboratory reports must be filed with the source documents. Clinically significant abnormal laboratory findings are those which are not associated with the underlying disease, unless judged by the investigator to be more severe than expected for the participants' condition.

All laboratory tests with values considered clinically significantly abnormal during participation in the study should be repeated until the values return to normal or baseline or are no longer considered clinically significant by the investigator or medical monitor.

If such values do not return to normal or baseline within a period of time judged reasonable by the investigator, the etiology should be identified and the sponsor notified.

All protocol-required laboratory assessments, as defined in Section 10.2 (Appendix 2) and the assessments described in Section 10.5 (Appendix 5) and Section 10.2.1, must be conducted in accordance with the laboratory manual and the SoA.

If laboratory values from non-protocol-specified laboratory assessments performed at the institution's local laboratory require a change in participant management or are considered clinically significant by the investigator (for example, SAE or AE or dose modification), then the results must be recorded in the CRF.

8.2.5. Self-monitoring of Blood Glucose

Self-monitoring of blood glucose is optional in this study. Insulin titration will be guided by real-time CGM readings from the Dexcom G6 CGM during this study. Dexcom G6 CGM has been approved by FDA for making clinical decisions. In case glucose alerts and readings from Dexcom G6 CGM do not match participant's symptoms, the participant can use a finger stick blood glucose value to make treatment decisions.

All participants will wear Dexcom G6 CGM throughout the study until the end of maintenance period. Calibrating Dexcom G6 CGM using finger stick measurement is not allowed. All participants should use the sensor code printed on the back of adhesive patch to calibrate when starting a new sensor.

8.2.6. Hypoglycemia

Participants will be trained about signs and symptoms of hypoglycemia, how to treat hypoglycemia, and how to discuss hypoglycemic events with investigators.

Hypoglycemia will be described using the following definitions:

- **Level 1:** Glucose <70 mg/dL (3.9 mmol/L) and \geq 54 mg/dL (3.0 mmol/L)
- **Level 2:** Glucose <54 mg/dL (3.0 mmol/L)
- **Level 3: Severe hypoglycemia:**

A severe event characterized by altered mental and/or physical status requiring assistance for treatment of hypoglycemia. Participants have altered mental status and cannot assist in their own care, may be semiconscious or unconscious, or experience coma with or without seizures, and require assistance of another person to actively administer carbohydrate, glucagon, or other resuscitative actions. Glucose measurements may not be available during such an event, but neurological recovery attributable to the restoration of blood glucose concentration to normal is considered sufficient evidence that the event was induced by a low blood glucose concentration.

- The determination of a hypoglycemic event as an episode of severe hypoglycemia, as defined above, is made by the investigator based on the medical need of the participant to have required assistance and is not predicated on the report of a participant simply having received assistance.
- All episodes of severe hypoglycemia must be reported as SAEs on the AE eCRF page and on the SAE eCRF page.

Any events of severe hypoglycemia categorized as level 3 per the evaluation of investigators will be collected from ICF signing to Visit 801.

Episodes of hypoglycemia categorized as level 1 or level 2 will be analyzed based on data from the CGM sensor session. Therefore, level 1 and level 2 hypoglycemic events do not need to be reported as an AE.

8.2.7. Safety Monitoring

The principle investigator will monitor safety and laboratory data throughout the study and should discuss safety concerns with the sponsor immediately upon occurrence or awareness of the concern to determine whether the participant should continue or discontinue study drug.

8.2.7.1. Hypersensitivity Reactions

Many drugs, but particularly biologic agents, carry the risk of systemic hypersensitivity reactions. If such a reaction occurs, the event will be reported as a spontaneous AE. Additional data describing each symptom should be provided to the sponsor in the eCRF.

Sites should have appropriately trained medical staff and appropriate medical equipment available when study participants are receiving study drug. It is recommended that participants who experience a systemic hypersensitivity reaction be treated per the local standard of care.

In the case of generalized urticaria or anaphylaxis, additional blood, or urine samples should be collected as described in Section 10.2.1. Laboratory results are provided to the sponsor via the central laboratory.

8.2.7.2. Hepatic Monitoring

If a participant develops symptoms that warrant liver function assessment, liver function tests as detailed in Section 10.5 should be performed. If these tests are abnormal, clinical and laboratory monitoring should be initiated by the investigator.

8.3. Adverse Events and Serious Adverse Events

Adverse events will be reported by the participant, or when appropriate, by a caregiver or surrogate..

The investigator and any qualified designees are responsible for detecting, documenting, and recording events that meet the definition of an AE or SAE and remain responsible for following up AEs that are serious, considered related to the study intervention or study procedures, or that caused the participant to discontinue the study intervention or the study (See Section 7).

8.3.1. Time Period and Frequency for Collecting AE and SAE Information

All AEs occurring after signing the ICF are recorded in the AE eCRF and assessed for serious criteria.

The SAE reporting to sponsor begins after the participant has signed the ICF and has received study drug. However, if an SAE occurs after signing the ICF, but before receiving LY900014, it needs to be reported ONLY if it is considered reasonably possibly related to study procedures.

All SAEs will be recorded and reported to the sponsor or designee immediately and under no circumstance should this exceed 24 hours, as indicated in Section 10.3 (Appendix 3). The investigator will submit any updated SAE data to the sponsor within 24 hours of it being available.

Investigators are not obligated to actively seek AE or SAE after conclusion of the study participation. However, if the investigator learns of any SAE, including a death, at any time after a participant has been discharged from the study, and he/she considers the event to be reasonably related to the study intervention or study participation, the investigator must promptly notify the sponsor.

8.3.2. Method of Detecting AEs and SAEs

The method of recording, evaluating, and assessing causality of AE and SAE and the procedures for completing and transmitting SAE reports are provided in Section 10.3 (Appendix 3).

Care will be taken not to introduce bias when detecting AEs and/or SAEs. Open-ended and nonleading verbal questioning of the participant is the preferred method to inquire about AE occurrences.

8.3.3. Follow-up of AEs and SAEs

After the initial AE or SAE report, the investigator is required to proactively follow each participant at subsequent visits or contacts. All SAEs, and AEs of special interest (as defined in Section 8.3.6), will be followed until resolution, stabilization, the event is otherwise explained, or the participant is lost to follow-up (as defined in Section 7.3). Further information on follow-up procedures is provided in Section 10.3 (Appendix 3).

8.3.4. Regulatory Reporting Requirements for SAEs

Prompt notification by the investigator to the sponsor of a SAE is essential so that legal obligations and ethical responsibilities towards the safety of participants and the safety of a study intervention under clinical investigation are met.

The sponsor has a legal responsibility to notify both the local regulatory authority and other regulatory agencies about the safety of a study intervention under clinical investigation. The sponsor will comply with country-specific regulatory requirements relating to safety reporting to the regulatory authority, Institutional Review Boards (IRB)/Independent Ethics Committees (IEC), and investigators.

An investigator who receives an investigator safety report describing a SAE or other specific safety information (for example, summary or listing of SAEs) from the sponsor will review and then file it along with the IB and will notify the IRB/IEC, if appropriate according to local requirements.

8.3.5. Pregnancy

Pregnancy (maternal or paternal exposure to study treatment) does not meet the definition of an AE. However, to fulfill regulatory requirements, any pregnancy should be reported following the SAE process described in Section 10.4 (Appendix 4) to collect data on the outcome for both mother and fetus.

Details of all pregnancies in female participants and, if indicated, female partners of male participants will be collected after the start of study intervention and until a period that is at least 5 terminal half-lives after the last dose.

If a pregnancy is reported, the investigator should inform the sponsor within 24 hours of learning of the pregnancy and should follow the procedures outlined in Section 10.4 (Appendix 4).

Abnormal pregnancy outcomes (for example, spontaneous abortion, fetal death, stillbirth, congenital anomalies, ectopic pregnancy) are considered SAEs.

8.3.6. Adverse Events of Special Interest

There are no adverse events of special interest (AESIs) in Study ITSZ.

8.3.7. Product Complaints

A product complaint is any written, electronic, or oral communication that alleges deficiencies related to the identity, quality, durability, reliability, safety, effectiveness, or performance of products provided in the study.

Sponsor collects product complaints on investigational products and drug delivery systems used in clinical studies in order to ensure the safety of study participants, monitor quality, and to facilitate process and product improvements.

Participants will be instructed to contact the investigator as soon as possible if he or she has a complaint or problem with the investigational product so that the situation can be assessed.

Product complaints will be reported by the investigator to the sponsor per the Product Complaint Form.

Note: Adverse events or SAEs that are associated with a product complaint will also follow the processes outlined in Section 8.3.3 and Section 10.3 (Appendix 3) of the protocol.

8.3.7.1. Time Period for Detecting Product Complaints

Product complaints that result in an AE will be detected, documented, and reported to the sponsor during all periods of the study in which the drug or device is used.

If the investigator learns of any product complaint at any time after a participant has been discharged from the study, and such incident is considered reasonably related to a drug or device provided for the study, the investigator will promptly notify the sponsor.

8.3.7.2. Prompt Reporting of Product Complaints to Sponsor

The Product Complaint Form will be available to the investigator on an investigator site portal and all product complaints will be reported according to the instructions on the form.

Additionally, the investigator will be supplied with product complaint reporting training materials.

8.3.7.3. Follow-up of Product Complaints

Follow-up applies to all participants, including those who discontinue study intervention. The investigator is responsible for ensuring that follow-up includes any supplemental investigations as indicated to elucidate the nature and/or causality of the product complaint. New or updated information will be recorded on the originally completed form with all changes signed and dated by the investigator and submitted to the sponsor.

8.4. Treatment of Overdose

In the event of an overdose, refer to the IB for LY900014, or to the product label for degludec.

Decisions regarding dose interruptions or modifications will be made by the investigator in consultation with the Medical Monitor based on the clinical evaluation of the participant.

8.5. Pharmacokinetics

Not applicable.

8.6. Pharmacodynamics

Not applicable.

8.7. Genetics

Not applicable

8.8. Biomarkers

Not applicable.

8.9. Immunogenicity Assessments

Not applicable.

8.10. Health Economics

Not applicable.

9. Statistical Considerations

9.1. Statistical Hypotheses

As an exploratory pilot dose optimization study, the primary objective of Study ITSZ is to evaluate the percentage of time with glucose values within target range (70 to 180 mg/dL, both inclusive) after 35 days of using the study titration scheme with LY900014 treatment and degludec.

The study will investigate if a more aggressive ICR is needed with LY900014 treatment for participants to reach the study-specific glucose target, compared to the “500 Rule” that is currently used in clinical practice.

9.2. Sample Size Determination

Approximately 34 participants will be assigned to study treatment such that 30 evaluable participants will complete the maintenance period, assuming a 10% dropout rate.

The study is not strictly powered to demonstrate a statistically significant change from baseline in the primary endpoint (percentage of time with glucose within 70 to 180 mg/dL) because of the exploratory nature of the study.

Using a standard deviation of 12%, the sample will provide approximately 80% coverage probability that the half-width of the 95% confidence interval of the change from baseline in the primary endpoint falls within 4.93%.

9.3. Populations for Analyses

The following populations are defined:

Population	Description
Entered	All participants who give informed consent
Enrolled	All participants who continue the study after Visit 2
Treated	All assigned participants who receive at least 1 dose of the assigned study treatment after Visit 3

9.4. Statistical Analyses

Statistical analysis of this study will be the responsibility of Lilly or its designee. Any change to the data analysis methods described in the protocol will require an amendment ONLY if it changes a principal feature of the protocol. Any other change to the data analysis methods described in the protocol, and the justification for making the change, will be described in the statistical analysis plan (SAP) or the clinical study report. Additional exploratory analyses of data will be conducted, as deemed appropriate.

9.4.1. General Considerations

Unless otherwise specified, all efficacy and safety analyses will be conducted on the Treated Population. Unless otherwise noted, all tests will be conducted at a 2-sided alpha level of 0.05, and confidence intervals will be calculated at 95%, 2-sided. Comparison between baseline and

endpoints will be performed at the full significance level of 0.05. No multiplicity adjustment will be made. Baseline is defined as the last non-missing measurement at or before the treatment assignment (Visit 3) unless otherwise specified.

An analysis of covariance (ANCOVA) will be used to analyze continuous variables that are planned to be collected only for baseline and endpoint. The model will include baseline as a covariate.

A restricted-maximum-likelihood-based, mixed model repeated measures (MMRM) analysis will be used to analyze continuous longitudinal variables collected only at baseline and more than one scheduled post-baseline visits according to SoA in Section 1.3. All the longitudinal observations at each scheduled post-baseline visit will be included in the analysis. The model for the analysis of the primary efficacy endpoint will include the fixed class effect of visit, and the random effect of patient. An unstructured covariance structure will be used to model the within-patient errors. Significance tests will be based on least-squares (LS) means and Type III tests. SAS PROC MIXED will be used to perform the analysis. If this analysis fails to converge, the following covariance structures will be tested in order:

- Toeplitz with heterogeneity
- Autoregressive with heterogeneity
- Compound symmetry with heterogeneous variances
- Toeplitz
- Autoregressive
- Compound symmetry without heterogeneous variances

The first covariance structure that converges will be used. The Kenward-Roger approximation will be used to estimate denominator degrees of freedom. If the analysis still does not converge with Compound symmetry without heterogeneous variances, only summary statistics will be provided.

For continuous measures, summary statistics will include sample size, mean, standard deviation, median, minimum, and maximum for both the actual and the change from baseline measurements. Least-square (LS) means and standard errors derived from the analysis models will also be displayed for the actual and the change from baseline measurements.

For categorical measures, summary statistics will include sample size, frequency, and percentages. No statistical analyses will be conducted for baseline and endpoint comparison.

All CGM outcome variables will only be derived for Visit 3 (baseline) and Visit 14 (endpoint) based upon the CGM data collected from valid CGM days, excluding data (if any) that are collected while patients are temporarily off Humalog during the lead-in period or temporarily off IP during the maintenance period. A valid CGM day to be counted into the calculation for a visit must have at least 70% of the total measures that are supposed to be obtained.

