9.4.5. Other Safety Analyses

Safety measures will include AEs, vital signs, and treatment exposure. Events that are newly reported after the first dose of IP used or reported to worsen in severity from baseline (details will be described in SAP) will be considered TEAEs.

Analyses of AEs will be descriptive and include all data collected during the treatment period. AEs during the lead-in period and the safety follow-up period will be provided in a listing.

Serious AEs, AEs reported as the reason for discontinuation from the IP or study, and TEAEs will be summarized in tables using the Medical Dictionary for Regulatory Activities (MedDRA) Preferred Term sorted by decreasing frequency. Treatment-emergent AEs will also be summarized by preferred term sorted by decreasing frequency within the SOC for all TEAEs and by maximum severity. For events that are gender-specific (as defined by MedDRA), the denominator and computation of the percentage will include only patients from the given gender. The number and proportion of patients with at least 1 event for each type of event will also be summarized.

In addition, time in hypoglycemic ranges will be assessed by CGM analyses.

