6.3. Handling of Dropouts or Missing Data

For CGM outcome variables only derived for Visit 3 (baseline) and Visit 14 (endpoint) based upon the CGM data, missing data will not be addressed. Only completers will be included in ANCOVA analysis.

For continuous variables collected at baseline and at Visit 14, missing data will not be addressed. Only completers will be included in ANCOVA analysis.

For continuous longitudinal variables collected at baseline and more than one scheduled post-baseline visits according to SoA in Section 1.3, missing data will be addressed by using a MMRM analysis. The MMRM model provides consistent estimator when data is missing at random. The model implicitly adjusts for missing data through a variance-covariance structure.

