6.10.3.1. Hypoglycemia

Hypoglycemia will be described using the following definitions:

- **Level 1:** Glucose <70 mg/dL (3.9 mmol/L) and ≥54 mg/dL (3.0 mmol/L)
- **Level 2:** Glucose <54 mg/dL (3.0 mmol/L)
- **Level 3: Severe hypoglycemia:**

Participants have altered mental status and cannot assist in their own care, may be semiconscious or unconscious, or experience coma with or without seizures, and require assistance of another person to actively administer carbohydrate, glucagon, or other resuscitative actions. Glucose measurements may not be available during such an event, but neurological recovery attributable to the restoration of blood glucose concentration to normal is considered sufficient evidence that the event was induced by a low blood glucose concentration.

- The determination of a hypoglycemic event as an episode of severe hypoglycemia, as defined above, is made by the investigator based on the medical need of the participant to have required assistance and is not predicated on the report of a participant simply having received assistance.
- All episodes of severe hypoglycemia must be reported as SAEs on the AE eCRF page and on the SAE eCRF page.

Any events of severe hypoglycemia categorized as level 3 per the evaluation of investigators will be collected from ICF signing to Visit 801.

Level 1 and level 2 hypoglycemia will be analyzed based on glucose data from the CGM sensor session. Derivation and analysis of Level 1 and Level 2 hypoglycemia (derived for duration (in minutes) and percentage of time in Level 1 or Level 2) and other CGM endpoints are described in Section 6.13.

Severe hypoglycemia will be collected as AEs in eCRF and all episodes of severe hypoglycemia will be considered as SAEs. Table ITSZ.6.4 provides detailed statistical methods for severe hypoglycemia. Summary statistics will be provided for severe hypoglycemia events from first dose to last dose of IP.

A listing of patients with at least 1 severe hypoglycemia reported (as SAE) from Visit 3 through Visit 801 will be provided.

A list of MedDRA PTs will be used for the narrow search of potential severe hypoglycemia in spontaneously reported AEs. The events identified through the search strategy that are also reported as SAEs will be summarized.

Table ITSZ.6.4. Summary of Analyses for Severe Hypoglycemia

Endpoint	Analysis Period	Statistical Method

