6.13. CGM Analyses

The analyses described in Section 6.13 will include data collected from first dose of Humalog used during the lead-in period to the last IP used during the treatment period, excluding data (if any) that are collected while patients are temporarily off Humalog or IP.

All CGM outcome variables will only be derived for Visit 3 (baseline) and Visit 14 (endpoint) based upon the CGM data collected from valid CGM days, excluding data (if any) that are collected while patients are temporarily off Humalog during the lead-in period or temporarily off IP during the maintenance period. A valid CGM day to be counted into the calculation for a visit must have at least 70% of the total measures that are supposed to be obtained.

[Table ITSZ.6.5](#) lists all numerical measures for CGM data.

To ensure that the CGM outcome variables are only calculated from CGM session days with sufficient data within the 24-hour, daytime (0600 hours to midnight), or nighttime (midnight to 0600 hours) periods, the following criteria will be used to determine a valid CGM session day to be counted into the calculation for a visit: minimum number of measures per day – at least 70% of the total measures that are supposed to be obtained, i.e., 70% of the 288 measures for the 24-hour period;

Similarly, for the by-meal outcome variables, the following criteria will be used to determine a valid CGM session day for a visit: minimum number of measures per day – at least 70% of the

total measures that are supposed to be obtained. For example, 70% of the 24 measures for the $iAUC_{0-2hr}$ after breakfast.

The definition and derivation of these variables are described in detail in [Appendix 1](#).

Table ITSZ.6.5. Outcome Measures of CGM Data

Category	Endpoints	24-Hour	Daytime ^a	Nighttime ^b	By Meal ^c
Efficacy Endpoint: Glucose in the Target Ranges					
	Duration (in minutes) and percentage of time with sensor glucose values within target range 70 to 180 mg/dL [3.9 and 10.0 mmol/L], both inclusive (Primary Efficacy Endpoint)	X	X	X	
Efficacy Endpoint: Incremental AUCs (iAUCs) (after the start of meals)					
	$iAUC_{0-1hr}$				X
	$iAUC_{0-2hr}$				X
	$iAUC_{0-3hr}$				X
	$iAUC_{0-4hr}$				X
Efficacy Endpoint: Mean Glucose Excursions (after the start of meals) ^d					
	mean sensor glucose excursions 0 to 1 hour				X
	mean sensor glucose excursions 0 to 2 hour				X
	mean sensor glucose excursions 0 to 3 hour				X
	mean sensor glucose excursions 0 to 4 hour				X

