The proportion of patients who have achieved the guidance (Battelino 2019) recommended CGM targets of glycemic control (Table ITSZ.6.6) during the lead in period (baseline) and the maintenance period (endpoint) will be summarized.

Table ITSZ.6.6. Guidance Recommended CGM Targets of Glycemic Control

Percentage of time with sensor glucose (24-hour)	Guidance Recommendation
target range	
70-180 mg/d.L (3.9-10.0 mmol/L, both inclusive)	>70%
hypoglycemia range	
<54 mg/dL (3.0 mmol/L)	<1%
hyperglycemia range	
>250 mg/dL (13.9 mmol/L)	<5%

Other than that, all continuous variables (actual and change from baseline, if applicable) will be analyzed by using the ANCOVA defined in Section 6.1.

In addition, the following standardized glucose summary reports from the ambulatory glucose profile (AGP) will be generated, based upon all the observed CGM data during the lead in period and the maintenance period, regardless of whether they are collected on valid CGM days:

- 24-hour period at individual patient level
- 24-hour period at the treatment level
- 0 to 4 hours relative to meal starting time, excluding data collected after the next meal event (if any is captured within the interval) at the treatment level
- 0 to 4 hours relative to meal starting time, by meal (breakfast, lunch, and dinner) and by infusion set wear day excluding data collected after the next meal event

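### Level 1 and level 2 hypoglycemia is left to CGM, but CGM variables are derived only for lead-in and maintenance, so the 35-day titration period has no planned level 1/2 summary

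*Protocol*

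**What the plan says.** Protocol 8.2.6 assigns level 1 and level 2 episodes to the CGM data and concludes: "Therefore, level 1 and level 2 hypoglycemic events do not need to be reported as an AE". Protocol 9.4.5 adds, among the safety analyses: "In addition, time in hypoglycemic ranges will be assessed by CGM analyses". SAP 6.10.3.1 agrees ("Level 1 and level 2 hypoglycemia will be analyzed based on glucose data from the CGM sensor session") and refers to SAP 6.13 for the derivation.

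The derivation rule is in protocol 9.4.1: "All CGM outcome variables will only be derived for Visit 3 (baseline) and Visit 14 (endpoint". SAP 6.1, SAP 6.13 and SAP Appendix 1 (9.1) repeat it. Under protocol 4.1.1, baseline CGM is the lead-in data and endpoint CGM is the maintenance data. The hypoglycemia safety rows of Table ITSZ.6.5 fall under this rule. The ambulatory glucose profile reports, which also use days that fail the valid-day test, are still "based upon all the observed CGM data during the lead in period and the maintenance period".

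For missing data, SAP 6.3 says of the CGM variables: "Only completers will be included in ANCOVA analysis". Table ITSZ.6.2 requires both a baseline and a post-baseline CGM observation, and the latter is Visit 14.

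Level 3 is handled differently: "Summary statistics will be provided for severe hypoglycemia events from first dose to last dose of IP".

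**The concern.** The reason given for not collecting level 1 and level 2 events as adverse events is that CGM will capture them. The analysis rule then removes that CGM analysis for the period in which basal dose, ICR and ISF are being changed about twice a week. What remains is a description of level 1/2 hypoglycemia before treatment, and again after settings have been fixed, in participants who got that far.

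This matters because the object of study is a titration scheme. The rationale (protocol 1.1, 2.1 and 4.3) is that faster-acting insulin might permit more aggressive mealtime dosing without more late post-meal hypoglycemia. Protocol 2.3.1 lists hypoglycemia first among the risks. As planned, the report could not say how much time below 70 or below 54 mg/dL occurred while the scheme was in progress, or whether those who stopped early had more of it.

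**Working it through.** **Inputs.** Titration 35 days and maintenance 11 days (protocol 1.1, 4.2). 34 assigned, 30 evaluable, 10% dropout (protocol 9.2). 288 sensor readings per full day (SAP 6.13). Sensor worn from Day -11 to Day 46 (protocol 4.1.1).

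**1. The plan's own figures.** The documents give no figure for hypoglycemia coverage. The sample size used below does reproduce: 30 / (1 - 0.10) = 33.3, rounded up to 34. Treatment length is 35 + 11 = 46 days.

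**2. Treatment time outside the derivation windows.**
- Days: 35 / 46 = 76.1% outside, 11 / 46 = 23.9% inside.
- Participant-days at full planned participation: 34 × 35 = 1,190 outside and 34 × 11 = 374 inside; 1,190 / 1,564 = 76.1%.
- Readings per participant at full wear: 35 × 288 = 10,080 outside, at most 11 × 288 = 3,168 inside.

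These are one ratio in three units. It depends little on how days are counted. With Day 0 as a separate day it is 36 / 47 = 76.6%. If Day 46 is dropped, because participants return to their own sensor and insulin at Visit 14, it is 35 / 45 = 77.8%.

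**3. Early leavers.** The plan allows for 34 - 30 = 4 non-evaluable participants. The documents do not say when they would leave, so between 0 and 4 could go during titration. Any who do have no Visit 14 value and drop out of every CGM hypoglycemia summary.

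**4. Text that might fill the gap.**

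| Place | What it offers | Does it give a titration level 1/2 summary? |
|---|---|---|
| SAP 6.13, opening | Scope is "data collected from first dose of Humalog used during the lead-in period to the last IP used during the treatment period" | No. The next paragraph restricts every variable to Visits 3 and 14 |
| SAP Appendix 1 (9.1), last line | Readings on IP in the treatment period are included | No. It is an inclusion rule and defines no titration variable |
| SAP 6.10.3 with Table ITSZ.6.3 | Hypoglycemia analyzed much as TEAEs are, over titration and maintenance | No. SAP 6.10.3.1 sends levels 1 and 2 to 6.13 and keeps the event analysis for severe episodes |
| SAP Appendix 1 (9.9) | How to compute an episode's duration | No. It gives no period, episode definition or summary |
| Protocol 9.4 / SAP 6.1 | Further exploratory analyses allowed | No. A general allowance is not a planned analysis |
| Protocol 10.3.1 | Findings worse than expected may be AEs | Only for such cases, at the investigator's judgment |

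**5. Illustration only, with assumed values.** Suppose a participant spends m% of maintenance below 54 mg/dL, with full wear and equal weight per day. The whole-treatment figure reaches 1% when the titration figure is (46 - 11m) / 35. For m = 0, 0.5 and 0.9 this gives 1.31%, 1.16% and 1.03%, or 18.9, 16.7 and 14.9 minutes a day (percentage × 1,440 / 100). A participant can thus meet the below-1% target of Table ITSZ.6.6 in maintenance and still exceed 1% over treatment. The SAP applies that target only to lead-in and maintenance, so the conclusion does not rest on this step.

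**The case against.** The strongest reply is that the plan analyzes what its endpoints specify. The endpoint for time below 54 mg/dL is exploratory and is defined for maintenance, when settings are meant to be stable. No stated objective goes unanswered, and this is a 34-participant exploratory pilot. That is correct and limits the weight of the point, but it does not explain why event reporting was waived for the whole study in favor of a CGM analysis that covers a quarter of treatment.

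A second reply is that participants are protected during titration: alerts are set, investigators can see CGM data at any time, and the glucose profile is reviewed at each visit. This also stands. The gap is in reporting, not in monitoring.

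Third, the missing summary could be produced afterwards under the exploratory allowance. It could, but a safety summary chosen after the data are seen is weaker than one specified beforehand.

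Fourth, the addition is not trivial: two metrics, three ranges, three clock periods and two windows make 2 × 3 × 3 × 2 = 36 variables. Under SAP Appendix 1 (9.2), however, minutes are the percentage multiplied by period length, so 18 are distinct, and the derivation already exists. The exclusion of off-IP readings needs no new rule, because the opening of SAP 6.13 and the end of Appendix 1 (9.1) already apply it across the treatment period. The boundary days do need to be defined.

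**Conclusion.** The concern holds and should be fixed. By an explicit rule, 35 of 46 treatment days (76%) have no planned level 1 or level 2 hypoglycemia summary, although the sensor data will have been collected. Participants who leave during titration contribute none after baseline; their number is not given and could be 0 to 4 if dropout is as planned. The day count uses the nominal schedule, and other ways of counting days leave it between 76% and 78%.

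The primary and secondary endpoints, the maintenance-period endpoint below 54 mg/dL and the level 3 analysis are unaffected. The documents do not show how much level 1/2 hypoglycemia to expect in titration, so no effect on a result can be estimated. The SAP's wider and narrower statements of the CGM window also need to be reconciled.

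**What to change.** Keep the Visit 3 and Visit 14 rule for the efficacy CGM variables in protocol 9.4.1 and in SAP 6.1, 6.13 and Appendix 1 (9.1), and state how it fits with the wider window that opens SAP 6.13. Then add a rule on these lines:

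> Percentage of time and minutes with sensor glucose below 54, 54 to 69 and below 70 mg/dL (24-hour, daytime, nighttime) will also be derived for the titration period (first IP dose to Visit 13) and for the whole treatment period (first to last IP dose), with readings taken while off IP excluded. Every Treated participant with one or more valid CGM days in the period is included, whether or not the participant completes. Results are summarized descriptively next to lead-in, with counts of participants and valid days.

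Say how Day 0 and the day of Visit 13 are allocated. Refer to the rule in SAP 6.10.3.1 and give it a row in Table ITSZ.6.2 that does not require a maintenance observation. Leave the post-meal windows at lead-in and maintenance, because meal start times are required in the Dexcom app only for Days -10 to -1 and 36 to 45.

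The cost is wording and a few descriptive tables from existing data, with no new visits or participants and no effect on the primary analysis. Protocol 9.4 lets changes that do not alter a principal feature be made in the SAP, so a separate protocol amendment may not be needed.
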